6.3.1 Reduction in Migraine Days per Month

Subjects are instructed to report headache occurrence, headache pain features and associated symptoms, aura occurrence, and medication used to treat headache or aura in the eDiary headache report every day in the OP, DBT, and OLE Phases.

Migraine days per month are assessed as "migraine days per 4 weeks" to correspond with the 4week visit schedule. Migraine days per month are based on 4-week intervals, and are prorated to account for missing migraine reports.

See Section 9.2.2 for the definition of eDiary efficacy data days, and Section 9.2.5 for the definition of migraine days.

6.3.1.1 Reduction in Migraine Days per Month in the DBT Phase: Primary Efficacy Endpoint

The number of migraine days per month in the DBT phase is examined relative to the number of migraine days per month in the OP for the DBT migraine analysis set, i.e., subjects with ≥ 14 days of eDiary efficacy data (not necessarily consecutive) in both the OP analysis period and ≥ 1 month (i.e., 4-week interval) in the on-DBT efficacy analysis period.

Months in the DBT phase are defined as follows:

- Month 1 (\leq 4 weeks; study days 1 to 28)
- Month 2 (> 4 to \leq 8 weeks; study days 29 to 56)
- Month 3 (> 8 to \leq 12 weeks; study days 57 to 84).

Analyses are based on eDiary efficacy dates in the OP and on-DBT efficacy analysis periods.

The number of migraine days per month is prorated to 28 days and derived as follows:

- OP: 28 × (total number of migraine days in the OP analysis period)/(total number of efficacy data days in the OP analysis period). Subjects must have ≥ 14 days of eDiary efficacy data (not necessarily consecutive) in the OP to be evaluable.
- Month (i.e., 4-week interval) in the on-DBT efficacy analysis period: 28 × (total number of migraine days in the month)/(total number of efficacy data days in the month). Subjects must have ≥ 14 days of efficacy data (not necessarily consecutive) in the specified month to be evaluable.
- Overall DBT: 28 × (total number of migraine days through Month 3 in the on-DBT efficacy analysis period)/(total number of efficacy data days through Month 3 in the on-DBT efficacy analysis period).

Missing Efficacy Data

The frequency table of missing efficacy data in the OP and DBT Phase is provided for the DBT efficacy analysis set, and displays the following categories:

- Included in the DBT migraine analysis set: ≥ 14 days of eDiary efficacy data (not necessarily consecutive) in both the OP and ≥ 1 month (i.e., 4-week interval) of the DBT Phase
 - Month 1: \leq 4 weeks *
 - Month 2: > 4 to ≤ 8 weeks *
 - Month 3: > 8 to ≤ 12 weeks *
- Excluded from the DBT migraine analysis set
 - \circ < 14 days of eDiary efficacy data in the OP
 - < 14 days of eDiary efficacy data in all 3 months of the DBT Phase.

In the categories marked with "*", subjects must have ≥ 14 days of efficacy data (not necessarily consecutive) in the specified month to be evaluable.

Descriptive Analyses

The table of values and changes (both absolute and percent) from the OP in the number of migraine days per month in the DBT Phase is provided for the DBT migraine analysis set, and summarizes parameters descriptively as continuous variables (including 2-sided normal 95% CIs for mean change) by treatment group and by pain intensity in each month of the DBT Phase and overall DBT. Pain intensity categories are (1) total (mild, moderate, severe, none, or not reported) and (2) moderate or severe. The table also presents results by subgroup level for all efficacy subgroups of interest described in Section 4.3.

In the percent change analyses, subjects must also have ≥ 1 migraine day (i.e., absolute not prorated to 28 days) of appropriate migraine severity in the OP analysis period to be included.

Treatment Group Comparisons

Analyses are based on DBT migraine analysis set and total pain intensity, unless otherwise specified.

Main Analysis: DBT Migraine Analysis Set

The main analysis of the primary endpoint uses a linear mixed effects model with repeated measures and the following attributes:

- Variables: change from the OP in number of total migraine days per month as the dependent variable; number of total migraine days per month in the OP as a covariate; treatment group, randomization stratum, month (i.e., Months 1 to 3 of the DBT Phase), and the month-by-treatment group interaction as fixed effects.
- Covariance structure for repeated measures accounting for within-subject correlated errors: assumed to be homogeneous across treatment groups and initially specified as unstructured. If the model fails to converge or cannot be fit with an unstructured covariance structure, then other covariance structures are specified in the following hierarchical order: Toeplitz (which has heterogenous variances and heterogenous correlations between elements); first-order autoregressive with heterogeneous variances; and first-order autoregressive with homogeneous variances.
- SE estimation method: Huber-White robust "sandwich" (refer to the Core SAP).

The table displays the following model estimates:

- Least-squares mean (LSM) change from OP, standard error (SE), and 95% CI by month and overall DBT for each treatment group
- Difference in LSM changes from OP between rimegepant and placebo, SE, 95% CI, and pvalue at each month and overall DBT. Results in the last month support the primary objective, results in the overall DBT support secondary objective #2, results in the first

month support secondary objective #3, and results in the second month support exploratory objective #1.

See Section 9.3.1 for example SAS code. Model estimates by randomization stratum (yes, no) are presented in the same table, using additional linear mixed effects models that exclude randomization stratum as a fixed effect.

The main analyses are repeated for moderate or severe pain intensity to support exploratory objective #1. All variables in the model are the same, except (1) change from the OP in number of moderate or severe migraine days per month is the dependent variable, and (2) number of moderate or severe migraine days per month in the OP is the covariate. The corresponding table has the same format.

The line plot displays the LSM change from OP in the number of total migraine days from OP per month on the y-axis versus month of the DBT Phase on the x-axis by treatment group. Error bars denote 95% CIs.

J2R Imputation Sensitivity Analysis: DBT Efficacy Analysis Set

A sensitivity analysis of the primary endpoint uses the same linear mixed effects model as the main analysis, but with jump to reference (J2R) to impute missing data (i.e., change from OP in the number of total migraine days per month) in Months 1 to 3 for the DBT efficacy analysis set. Placebo is considered the "reference".

The analysis is performed using the following steps:

- 1) Data are imputed under J2R using specific multiple imputation SAS macros.^{1, 2}
 - a) Subjects with < 14 days of eDiary efficacy data in a specified month in the on-DBT efficacy analysis period have missing data imputed in that month.
 - b) Data imputation is applied to each treatment group.
 - c) The imputation model uses the following variables: number of total migraine days per month in the OP, age, sex, randomization stratum, and treatment group.
 - d) The macros are run in the following order: %part1A; %part1B using n = 200 data sets (Ndraws parameter) and n = 100 for Markov chain Monte Carlo (MCMC) chain thinning (thin parameter); %part2A; and %part2B. Note that Ndraws and thin parameters may be modified as needed (e.g., to decrease MCMC error and autocorrelation).
- 2) Each imputed data set in step 1 is analyzed using the same model from the main analysis (see Section 9.3.1).
- 3) Results from each model analysis in step 2 are combined to produce a pooled difference in LSM change, SE, 95% CI, and p-value using SAS proc mianalyze.

The corresponding table has the same format as the one for the main analysis.

Tipping Point Sensitivity Analysis: DBT Efficacy Analysis Set

A tipping point sensitivity analysis is performed for the DBT efficacy analysis set, and only if the p-value ≤ 0.05 for the treatment group comparison for the main analysis of the last 4 weeks of the DBT Phase.

The analysis is performed using the following steps:

- 1) A shift parameter of $\delta = 0$ is selected.
 - a) Data are imputed under the missing not at random (MNAR) assumption for the rimegepant treatment group with a shift adjustment and the missing at random (MAR) assumption for the placebo treatment group using SAS proc mi for n = 30 data sets.^{1,2}
 - i) Subjects with < 14 days of eDiary efficacy data in a specified month in the on-DBT efficacy analysis period have missing data imputed in that month.
 - ii) Data imputation is applied to each treatment group.
 - iii) The fully conditional specification (FCS) method is used with regression to impute data at Months 1 to 3.
 - iv) The imputation model specifies variables in the following order: changes from OP in the number of total migraine days per month at Months 1 to 3, number of total migraine days per month in the OP, age, sex, randomization stratum, and treatment group.
 - v) A shift of δ is applied to imputed data only for subjects in the rimegepant treatment group.
 - b) Each imputed data set in step 1a is analyzed using the same model from the main analysis (see Section 9.3.1).
 - c) Results from each model analysis in step 1b are combined to produce a pooled difference in LSM change, SE, 95% CI, and p-value using SAS proc mianalyze.
- 2) The p-value for the treatment group comparison of the last 4 weeks of the DBT Phase compared to 0.05.
 - a) If p-value ≤ 0.05 , then δ is incremented by 0.1, and step 1 is repeated.
 - b) If p-value > 0.05, then the iterative process stops, and the last δ used becomes the tipping point.

For each shift parameter, the same statistics are provided as those in the main analysis, but only for the last 4 weeks of the DBT Phase. Results across all shift parameters are displayed together in the same table.

Subgroup Analyses

Subgroup analyses of the primary endpoint will use the same linear mixed effects model specified for the main analysis of the primary endpoint. The following model estimates will be reported by subgroup of historical chronic migraine according to ICHD 3rd edition (yes or no) (Section 4.3). P-values are presented only for descriptive purpose.

- LSM change from OP, SE, 95% CI by month in the DBT Phase and overall DBT for each treatment group
- Difference in LSM changes from OP between treatment groups (rimegepant placebo), SE, 95% CI, and p-value at each month and overall DBT.

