5 SAMPLE SIZE, POWER, AND TYPE I ERROR

The study randomizes approximately 245 subjects per treatment arm to obtain roughly 225 evaluable subjects per treatment arm.

With a sample size of roughly 490 subjects randomized, and 245 subjects per group, we expect roughly 225 evaluable subjects per group in the efficacy data set. Assuming rimegepant provides roughly a 1 day advantage over placebo on the primary endpoint, a common standard deviation of 3.75 days, and a 2-sided alpha level of 0.05, then the study will have roughly 80% power on the primary endpoint. The estimates for the change in migraine days per month and the standard deviation are consistent with publicly available information from another investigational oral CGRP antagonist for this indication.

Type I error will be controlled by using a hierarchical gate keeping procedure. If the primary endpoint is significant at the 2-sided alpha level of 0.05, then secondary efficacy or outcomes research endpoints are tested hierarchically, each at a 2-sided alpha level of 0.05, in the order in which they appear in Section 3.2.2. Thus, a secondary efficacy or outcomes research endpoint is tested only if the preceding secondary endpoint in the hierarchy is determined to be significant (i.e., p-value ≤ 0.05). If a test in the hierarchy is not significant, then any further tests on endpoints in the sequence have p-values presented only for descriptive purposes, and no conclusions are drawn from those results. Note that secondary safety endpoints are not tested.

For exploratory endpoints, no attempt is made to adjust for multiplicity. Any exploratory endpoints for which p-values are produced are evaluated at an unadjusted, 2-sided alpha level of 0.05 and presented only for descriptive purposes.

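### In the C4951021 SAP, the tipping-point analysis uses 30 imputations on a 0.1-day grid, leaving Monte Carlo noise of about one to two and a half grid steps; 200 imputations and one fixed seed would cut it by about 61%

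*SAP*

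**What the plan says.** Section 6.3.1.1 of the SAP gives two missing-data sensitivity analyses for the change in migraine days per month in Weeks 9 to 12.

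- **Tipping point.** It runs only when the main comparison has p ≤ 0.05. Imputation is by fully conditional specification, "using SAS proc mi for n = 30 data sets". The shift δ "is applied to imputed data only for subjects in the rimegepant treatment group". It starts at 0. While p ≤ 0.05, "then δ is incremented by 0.1, and step 1 is repeated"; once p exceeds 0.05, "then the iterative process stops, and the last" shift tried is taken as the tipping point. Estimates, intervals and p-values for every shift go into one table.
- **Jump to reference (J2R).** The same endpoint and analysis set are imputed "using n = 200 data sets (Ndraws parameter"), and the SAP allows that setting to be changed to lower simulation error.

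The tipping-point steps contain no comparable allowance. The SAP text names no seed and does not say whether one seed serves all shifts. It refers to a Core SAP that is not among the documents.

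**The concern.** The tipping point is where a pooled p-value crosses a threshold, so Monte Carlo error in the pooled estimate carries straight through to δ. Because the shift touches only imputed rimegepant values, one 0.1-day step moves the treatment difference by only 0.1 times the missing fraction. When few values are missing, the noise from 30 imputations can be worth several steps. The same data with another seed would then give a different tipping point.

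A fixed seed makes one run repeatable; it does not make the figure more precise. If a new seed were drawn at each shift, a first-crossing rule would also tend to stop early. What is at stake is the precision of one reported sensitivity figure.

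**Working it through.** **Inputs from SAP Section 5.** "The study randomizes approximately 245 subjects per treatment arm to obtain roughly 225 evaluable subjects per treatment arm"; expected difference 1 day, SD 3.75 days, two-sided alpha 0.05, roughly 80% power.

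**The plan's own figure.** 1 / (3.75 × √(2/225)) = 2.83, and Φ(2.83 − 1.96) = 0.807. The stated power is reproduced.

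**Missing fraction.** 20/245 = 8.2%. The documents give this only indirectly, so f = 5% to 20% at Month 3 is taken as an assumed range.

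**Closed form.** This ignores information from earlier months, so it runs somewhat high.

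- Between-imputation variance of the Month 3 difference: B = 2·f·SD² / (n(1 − f)) = 2 × 0.0816 × 14.06 / 225 = 0.0102.
- Monte Carlo SD of the pooled difference with m = 30: √(0.0102/30) = 0.018 day.
- Effect of one step on the difference: 0.082 × 0.1 = 0.008 day. The noise is worth more than two steps.
- On the δ scale: √(B/m)/f = 0.018/0.082 = 0.23 day with m = 30, and 0.09 day with m = 200.
- With m = 30 at other fractions: 0.28 day at 5%, 0.19 at 12%, 0.155 at 20%.

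**Simulation, shift applied to Month 3 only.** 245 per arm, true effect 1 day, SD 3.75, three months with monotone dropout, Bayesian sequential-regression imputation, Month 3 ANCOVA with sandwich SE (standing in for the mixed model), Rubin pooling, 0.1 grid. Between-month correlation of 0.5 to 0.85 is assumed. There were six trials per setting, kept only if p was below 0.03 at zero shift, with repeated imputation sets drawn for each trial. The SD is over seeds for fixed trial data.

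| Missing | SD, m = 30 | SD, m = 200 | Two seeds differ by more than one step, m = 30 | Same, m = 200 |
|---|---|---|---|---|
| 5% | 0.19–0.26 | 0.08–0.10 | 57–68% | 17–31% |
| 8.2% | 0.16–0.20 | 0.07–0.09 | 50–62% | 8–19% |
| 12% | 0.13–0.19 | 0.06–0.08 | 43–56% | 6–14% |
| 20% | 0.12–0.16 | 0.06–0.07 | 36–48% | 3–10% |

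The central 95% range over seeds is 0.45 to 1.0 day with 30 imputations and 0.17 to 0.38 day with 200.

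**Simulation, shifted earlier months feeding later imputations.** With 30 imputations, correlation 0.7 and true effect 1.3 days, the SD is 0.11–0.14 day at 8.2% missing and 0.09–0.11 at 15%. By normal approximation the difference between two seeds has SD √2 × 0.09 = 0.13 to √2 × 0.14 = 0.20 day. Differing by more than one step on the grid means exceeding about 0.15, which has probability of about 24% to 45%.

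**Effect of 200 imputations.** √(30/200) = 0.39, so the SD falls by 61% and the variance by 85%.

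**A new seed at each shift.** With 30 imputations the search stops 0.04 to 0.17 day early on average; with 200 the bias is at most 0.02 day.

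**The case against.** The strongest reply is that no decision turns on this. The analysis is secondary to a test that already has p ≤ 0.05. The whole δ path is tabulated, so a reader is not left with one number, and J2R examines the same endpoint separately with 200 imputations. At 8.2% missing, the median simulated tipping points were 3.0 to 8.0 days, so the noise is small beside them: 0.18/3.0 = 6% and 0.16/8.0 = 2%. All of this stands, and it is why the point is minor.

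The size also depends on a reading that the SAP leaves open. It imputes Months 1 to 3 from one another and applies δ to imputed data, without saying whether shifted earlier months feed later ones. If they do, the noise falls to about one step. It does not vanish.

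The comparison with J2R is loose: the J2R allowance concerns settings of a different imputation routine. It is a precedent for 200, not proof that 30 is an error. A seed rule may exist in the Core SAP, but it would give repeatability only.

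A reader might infer that the tipping point is irreproducible, or that it is the headline measure of robustness. The documents support neither. The 0.1 is a search increment, not a claimed precision; a fixed seed would reproduce the run; and nothing in the SAP ranks this figure above the other results.

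**Conclusion.** The point holds as a minor matter of precision. With 30 imputations the Monte Carlo SD of the reported δ is about 0.12 to 0.26 day if only Month 3 is shifted, and about one step (0.09 to 0.14 day) if shifts carry forward. Seeds can often disagree by more than one step.

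This rests on the assumed 5% to 20% missing at Month 3 (8.2% from the SAP's own counts), SD 3.75, the assumed between-month correlations, and an ANCOVA stand-in for the mixed model.

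The interpretation would rarely change. The exception is a main result only just below 0.05, where the tipping point could be a few tenths of a day and the noise of similar size. The simulated trials with p below 0.03 do not cover that case directly.

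It would be wrong to infer that the primary test is at risk, or that the finding concerns the supplied protocol's endpoint. That protocol (C4951022) has pain freedom at 2 hours as its primary endpoint, whereas this SAP is for C4951021. The mismatch between the two documents is a separate and much larger matter.

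**What to change.** In the tipping-point steps of SAP Section 6.3.1.1, raise the number of imputed data sets from 30 to at least 200, and state one prespecified seed to be held constant across all δ values. It would also help to say whether shifted earlier months feed later imputations.

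This brings the Monte Carlo SD to about one step or less (0.06 to 0.10 day with a Month 3 shift). It does not make the figure exact to 0.1 day: the central 95% range over seeds would still span about two to four steps.

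The cost is one number, one or two sentences, and computing time: 200/30 = 6.7 times as many model fits. Reaching δ = 6 takes 61 shifts, so 61 × 200 = 12,200 fits instead of 61 × 30 = 1,830.

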6.3.1.2 Reduction in Migraine Days per Month in the OLE Phase

The number of migraine days per month in the OLE Phase is examined relative to the number of migraine days per month in the OP for the OL rimegepant migraine analysis set, i.e., subjects with ≥ 14 days of eDiary efficacy data (not necessarily consecutive) in the OP analysis period, ≥ 1 month (i.e., 4-week interval) in the on-DBT efficacy analysis period, and ≥ 1 month in the on-OL rimegepant efficacy analysis period.

Months in the OLE Phase are defined as:

- Month 1 (> 12 to \leq 16 weeks; study days 85 to 112)
- Month 2 (> 16 to \leq 20 weeks; study days 113 to 140)
- Month 3 (> 20 to \leq 24 weeks; study days 141 to 168)
- Month 4 (> 24 to \leq 28 weeks; study days 169 to 196)
- Month 5 (> 28 to \leq 32 weeks; study days 197 to 224)
- Month 6 (> 32 to ≤ 36 weeks; study days 225 to 252)
- Month 7 (> 36 to \leq 40 weeks; study days 253 to 280)
- Month 8 (> 40 to \leq 44 weeks; study days 281 to 308)
- Month 9 (> 44 to \leq 48 weeks; study days 309 to 336)
- Month 10 (> 48 to \leq 52 weeks; study days 337 to 364).

Analyses are based on eDiary efficacy dates in the OP analysis period and on-OL rimegepant efficacy analysis period.

The number of migraine days per month are to 28 days, and derived as follows:

- OP: See Section 6.3.1.1.
- Month (i.e., 4-week interval) in the on-OL rimegepant efficacy analysis period: 28 × (total number of migraine days in the month)/(total number of efficacy data days in the month).
 Subjects must have ≥ 14 days of eDiary efficacy data (not necessarily consecutive) in the specified month to be evaluable.
- Overall OL rimegepant: 28 × (total number of migraine days through Month 10 in the on-OL rimegepant efficacy analysis period)/(total number of efficacy data days through Month 10 in the on-OL rimegepant efficacy analysis period).

Missing Efficacy Data

The frequency table of missing efficacy data in the OP and OLE Phase is provided for the OL rimegepant efficacy analysis set by treatment group/OL rimegepant and overall, and displays the following categories:

- Included in the OL rimegepant migraine analysis set: ≥ 14 days of eDiary efficacy data (not necessarily consecutive) in the OP, ≥ 1 month (i.e., 4-week interval) of the DBT Phase, and ≥ 1 month of the OLE Phase
 - Month 1: > 12 to ≤ 16 weeks *
 - o Additional months defined previously
 - Month 10: > 48 to \leq 52 weeks *
- Excluded from the OL rimegepant migraine analysis set
 - \circ < 14 days of eDiary efficacy data in the OP
 - \circ < 14 days of eDiary efficacy data in all 3 months of the DBT Phase (see Section 6.3.1.1)
 - \circ < 14 days of eDiary efficacy data in all 10 months of the OLE Phase.

In the categories marked with "*", subjects must have ≥ 14 days of eDiary efficacy data (not necessarily consecutive) in the specified month to be evaluable.

Descriptive Analyses

Analyses are based on the OL rimegepant migraine analysis set, unless otherwise specified.

The table of values and changes (both absolute and percent) from the OP in the number of migraine days per month in the OLE Phase is provided, and summarizes parameters descriptively as continuous variables (including 2-sided 95% CIs for mean change) by treatment group/OL rimegepant and overall and by pain intensity (total; moderate or severe) in each month of the OLE Phase and overall OL rimegepant. Results support exploratory objective #4.

A line plot displays the mean change from OP in the number of total migraine days per month on the y-axis versus month (Month 1 to 10) of the OLE Phase on the x-axis by treatment group/OL rimegepant. Another line plot displays the mean change from OP in the number of total migraine days per month on the y-axis versus month (Month 1 to 13) of the DBT and OLE Phases on the x-axis for the DBT migraine analysis set by (1) treatment group during the DBT Phase and (2) overall for the OLE Phase. Error bars denote 95% CIs.

In the percent change analyses, subjects must also have ≥ 1 migraine day (i.e., absolute not prorated to 28 days) of appropriate severity in the OP analysis period to be included.

